## HRP-503 - Template – Protocol

not be conducting their own review. They agreed that MSU IRB will oversee this study. University of Michigan IRB is waiting for MSU IRB approval in order to file a "Requesting Review by a Non-UM IRB" application.

Recruitment and eligibility follow-up will be performed by trained research assistants and personnel.

***CLICK IRB: Upload the recruitment materials to the Consent Forms and Recruitment Materials SmartForm page, Question 2.***

**11B.** The study team will obtain for the purpose of screening, recruiting, or determining the eligibility of prospective subjects (please select the appropriate option(s)):  Not Applicable

Information through oral or written communication with the prospective subject or legally authorized representative. Before the information is obtained for the purpose of screening, recruiting, or determining eligibility, consent:  will be obtained.  will not be obtained. *Please describe screening consent procedures in Question 12.*

Identifiable private information or identifiable biospecimens by accessing records or stored identifiable biospecimens. Before the information is obtained for the purpose of screening, recruiting, or determining eligibility, consent:  will be obtained.  will not be obtained. *Please describe screening consent procedures in Question 12.*

*Note: The revised Common Rule permits an exception from informed consent for screening, recruiting, or determining eligibility when certain criteria are met; this exception does not apply to studies subject to the Pre-2018 Common Rule Requirements and/or studies regulated by the U.S. Food and Drug Administration (FDA).*

**11B1.** Please explain your selection(s).

We need to collect information in order to screen for major psychological and physical health problems as well as other criteria such as age, capabilities and willingness to participate in a longitudinal study, willingness to show ID over HIPPA compliant zoom, no COVID-19 diagnosis, English as their primary language, and experiencing moderate amount of COVID-19 related stress and anxiety.

### 12. Consent Process.

**12A.** If the study involves adults, consent will be obtained from (select appropriate option(s)):  Not Applicable

All subjects  
 Some subjects  
 No subjects (consent will not be obtained)

***CLICK IRB: Upload the consent document, script, etc. (including translations) to the Consent Forms and Recruitment Materials SmartForm page, Question 1.***

**12B.** If the study involves children, parental permission will be obtained from (select appropriate option(s)):  Not Applicable

Both parents or guardians (unless one parent is deceased, unknown, incompetent, or not reasonably available, or when only one parent has legal responsibility for the care and custody of the child)  
 One parent or guardian  
 Will not be obtained

*CLICK IRB: Upload the parental permission forms to the Consent Forms and Recruitment Materials SmartForm page, Question 1.*

**12C.** If the study involves children, child assent will be obtained from (select appropriate option):  Not Applicable

- All children
- Some children
- Will not be obtained

*CLICK IRB: Upload the child assent form to the Consent Forms and Recruitment Materials SmartForm page, Question 1.*

**12D.** Describe the consent process, including an explanation of your selection(s) above. If the study involves screening activities, please describe whether consent will be obtained and if consent will not be obtained, explain how the screening data will be used. If only some subjects will provide consent, explain who will or will not provide consent. If only some children will provide assent, explain which children will and will not provide assent.

The consent process will happen two times. First, consent will be obtained before the prescreening questionnaire is administered. The prescreening questions will be administered via an online survey through the Qualtrics platform. Once potential participants complete the survey, trained research assistants and personnel will determine if participants are eligible to be part of the study. Those who are not eligible will be sent an email thanking them for their participation. Those who are eligible will be contacted in order to set up a meeting for a potential enrollment.

For those who are eligible, participants will be provided with more details regarding the study to determine if they wish to participate. The consent process will involve a detailed description of the study, study expectations, and study payment. Participants will be told that they can withdraw from the study at anytime. A research assistant will walk participants through the consent process over the phone to ensure that they understand what the study entails. They will indicate consent through an online platform.

**12E.** If consent will not be obtained, explain why. Describe why the research could not be practically carried out if consent was required. If the research involves identifiable private information or identifiable biospecimens, describe why the research could not practically be carried out without using such information or biospecimens in an identifiable format.  Not Applicable

**12F.** If your study involves use of a consent form, complete i, ii, and iii.  Not Applicable

**12Fi.** Select the appropriate option(s) below for the documentation of consent.

- Will use a written consent document signed by subjects
- Will use a short form written consent document signed by subjects
- Will not obtain a signed consent document for some subjects
- Will not obtain a signed consent document for all subjects

**12Fii.** Describe when and how the subject will receive a copy of the consent form.

We will send a pdf copy of the consent form through email. We will also send them a link online in order for them to click yes or no.

**12Fiii.** If subjects will not be signing the consent document, please explain why. If some subjects will not sign the consent document, explain who will and will not sign the consent.  Not Applicable

Due to COVID-19, this study will be conducted online. As such, to ease participant burden, we will not obtain physical signatures from our participants. They will indicate consent by clicking yes on a digital version of the consent form.

**12G.** If the study involves cognitively impaired adults, explain the process to determine whether a subject is capable of consent, use of any legally authorized representative(s), and any assent process.  Not Applicable

*CLICK IRB: Upload any assessment tools to the Supporting Documents SmartForm page.*

**13. Coercion or Undue Influence.**

**13A.** If some or all of the subjects are likely to be vulnerable to coercion or undue influence, such as children, prisoners, pregnant women, mentally disabled persons, individuals with impaired decision-making capacity, or economically or educationally disadvantaged persons, describe additional safeguards that have been included in the study.  Not Applicable

**13B.** If you or your study team are associated with the subjects (e.g. your students, employees, colleagues, patients), explain the nature of any association and measures taken to protect subjects' rights, including safeguards against any coercion or undue influence (e.g. pressure a subject might feel to participate based on the association).  Not Applicable

**14. Privacy.**

How will subjects' privacy be protected? Consider the number of individuals interacting with the subject or subject's records, location of consent process and study, presence of individuals not associated with the study, sensitivity of the research.

Participant demographic information and name will be stored in a password-protected electronic document in a password protected computer. The data collected will not be stored with identifying information. We will assign a unique subject ID to label the study data and the key that links this unique ID to identifying information will be kept separately and securely from the data. It will be stored in a password-protected document.

The survey will only be accessed with a username and password by trained personnel. We will keep this data until after the full research period is over (5 years), after which it will be deleted. The consent process and the entirety of the experiment will take place online via phone call and for one condition, via an encrypted, password protected Zoom call.

Only the primary investigator, trained lab coordinators, graduate students, post-docs, and trained undergraduate research assistants will interact with the participant.

Each participant will be enrolled by one trained lab member.

**15. Withdrawal of Subjects.**  Not Applicable

## HRP-503 - Template – Protocol

If there are any anticipated circumstances where the researcher will withdraw subjects from the study regardless of the subject's wishes, describe the circumstances and the procedures when subjects are withdrawn from the study.

The participant will take a total of 4 surveys spanning 17 to 20 days. It is very important that participants take the first two surveys and the last survey (First, Second, and Fourth) or they will not be able to proceed with the study. The first two surveys help us establish baseline psychological and physical health and if they do not take it, we will not be able to do anything meaningful with the rest of their data. They really can only miss the Third Survey.

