Our assumption of a d effect size of .60 is a liberal assumption based on the literature in which the d effect size between a non-deceptive placebo and a no treatment control ranges from .30 to 1.00. The most relevant non-deceptive placebo study is El Brihi et al. (2019) in which they tested the effects of non-deceptive placebos on emotional distress and positive mental well-being. Comparing two types of non-deceptive placebos versus a control showed a non-deceptive placebo effect that ranges from a Cohen's d of .78 to 1.01 on emotional distress. Comparing two types of non-deceptive placebos versus a control showed a non-deceptive placebo effect that ranges from a Cohen's d of .55 to .93 for psychological well-being. As such, we estimate that a d effect size of .60 between a control group and our non-deceptive placebo group because our primary outcomes is also emotional distress and psychological well-being. A .60 d effect size is within a reasonable range of what is expected regarding a non-deceptive placebo effect on emotional distress. This will allow us to run approximately 50 in each condition, which is more than the sample size of the El Brihi et al. (2019) study in which they had n = 29 in the control condition and n = 30 and n = 31 in each of the non-deceptive placebo condition.

For our primary outcomes, we plan to run a 2 (Group) by 3 (Time: Time 2, Time 3) mixed factorial ANOVA (while controlling for baseline levels) followed by independent pairwise comparisons at each of time point. When possible, we plan to use multiple imputation methods to account for missing data. If a participant is missing data from 2 or more time points for our primary outcome, they will be removed for analyses. If a person is unresponsive for 5 days, we will consider them a dropout. We will send a final letter indicating that we apologize for their drop

and that they can contact us if they need anything and provide them resources if they require it. If participants wants to drop out, we can inquire why and offer them resources and contact information for future studies.

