Clinical Trial Statistical Analysis Plan

Title: Effects of Open-label Placebos Administered Through Telehealth on COVID-related Stress, Anxiety, and Depression

Brief Title: Effects of Open-label Placebos on COVID-related Psychological Health

Study Sponsor: Michigan State University

Principle Investigator:

Name: [name]

Official Title: Professor of Psychology

Affiliation: Michigan State University

[contact]

Email: [contact]

NCT Number: NCT05035550

Version Date: 1.22.21

Statistical Analysis Plan

All analyses were conducted on SPSS version 26 (IBM, Armonk, NY). Prior to our primary analyses, we first interpolated missing data using a maximum likelihood estimation (MLE). Second, we conducted an independent sample t-test on baseline measures of each primary outcome measure to ensure that the control and open-label placebo group did not differ prior to the administration of the intervention.

The primary outcomes at the endpoint (reduction in COVID stress, perceived stress, anxiety, and depression) were calculated using change from baseline scores (endpoint minus baseline) with positive numbers indicating greater reduction in symptoms at endpoint. First, each primary outcome was submitted to a one-way analysis of covariance (ANCOVA), with group as the independent variable and the mean baseline score for each outcome measure submitted as a covariate to control for variability in baseline scores (Lembo et al., 2021; Van Breukelen, 2006). We reported outlier detection procedures and additional robust analyses in the Supplementary Materials. Effect sizes for pairwise comparisons were calculated using Cohen's d. Secondary outcomes were analyzed using descriptive statistics and t-tests. All significance tests were analyzed at $p = .05$.

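### Protocol section 15 puts out a willing participant who misses only the Second Survey, whom the section 9Bii analysis rule would keep; the two rules need to become one.

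*Protocol*

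**What the plan says.** Protocol section 15 (Withdrawal of Subjects) answers a form item about when "the researcher will withdraw subjects from the study regardless of the subject's wishes". It first sets the schedule: "The participant will take a total of 4 surveys spanning 17 to 20 days". Participants must "take the first two surveys and the last survey (First, Second, and Fourth) or they will not be able to proceed with the study", and "They really can only miss the Third Survey". The reason given for requiring the early surveys is that "if they do not take it, we will not be able to do anything meaningful with the rest of their data". Their role is described in these terms: "The first two surveys help us establish baseline psychological and physical health".

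Protocol section 9Bii sets the analysis rule: "If a participant is missing data from 2 or more time points for our primary outcome, they will be removed for analyses". It also plans multiple imputation where possible, and has a separate dropout rule for five days without response.

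The SAP handles missing data by maximum likelihood. It analyses change from baseline to endpoint by ANCOVA, with "the mean baseline score for each outcome measure submitted as a covariate to control for variability in baseline scores". It has no rule on missed surveys or withdrawal. The two grounds for termination in Protocol section 16A (significant stress with a wish for another treatment, and no longer wishing to take part) do not include a missed survey.

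**The concern.** The two sections disagree on who is followed to the endpoint. Section 15 treats one missed early survey as fatal and justifies this on analytic grounds: the later data would be useless. Section 9Bii takes the opposite analytic position, since it tolerates one gap and plans to impute.

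What is at stake depends on when the Second Survey occurs. If it comes after allocation, section 15 excludes randomised people according to early engagement. Participants know their group, and engagement may differ between a pill arm and an assessment-only arm, so the exclusions need not balance. If it comes before allocation, the rule costs recruits and does not bias the comparison. Either way, staff and analysts following different sections would handle the same person differently.

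**Working it through.** **1. The rules side by side**, counting each survey as one time point.

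| Missed | Section 15 | Section 9Bii |
|---|---|---|
| First only | out | kept |
| Second only | out | kept |
| Third only | stays | kept |
| Fourth only | out | kept |
| Any two | out | removed |

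The rules disagree on 3 of the 4 single-miss patterns. The Second Survey is the one that matters most: a missed Fourth leaves no later survey to lose, and the endpoint itself is absent.

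**2. Sequence.** Someone who misses the Second Survey and is put out never takes the Third and Fourth. One missed survey becomes three, and section 9Bii then removes a person it would have kept.

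**3. Does this depend on how surveys map to time points?** The documents give no mapping; section 9Bii announces three time levels but names only Time 2 and Time 3. Suppose the First and Second Surveys together form Time 1, the Third is Time 2 and the Fourth is Time 3. Missing the Second then leaves at most one time point missing (Time 1), so the person is kept. After withdrawal Times 2 and 3 are missing, so the person is removed. The conflict stands under this mapping too.

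**4. Timing.** Section 9A gives two weeks of pills and section 15 gives 17 to 20 days in all. That leaves 17 − 14 = 3 to 20 − 14 = 6 days, enough for two surveys before pills start. No section places allocation relative to the Second Survey.

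**5. Power, for scale only.** Section 9Bii gives d = .60, power .80, alpha .05 and 50 per arm. An exact two-sided t-test needs 44.6, so 45 per arm. Fifty is more than these inputs require; it is also the budget figure, and equals 45/(1 − .10) if an unstated 10% allowance is assumed. This is not an error that bears on the point.

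No missed-survey rate is given, so 0% to 20% loss in both arms is assumed:

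| Loss | n per arm | Power, unadjusted t-test |
|---|---|---|
| 0% | 50 | .844 |
| 5% | 47.5 | .825 |
| 10% | 45 | .804 |
| 15% | 42.5 | .780 |
| 20% | 40 | .755 |

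The SAP plans ANCOVA. If d is scaled by the raw SD and the baseline–endpoint correlation is r (assumed), the effective size is .60/√(1 − r²). At r = .5 this is .60/.866 = .693, and 40 per arm give power .864. At r = .7 it is .60/.714 = .840, and 40 per arm give .960. At r = .5, 34 per arm suffice for .80, which allows 50 − 34 = 16 losses per arm.

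**6. Information in a First-Survey-only baseline**, if the First Survey carries the outcome scale and all surveys correlate equally at r (assumed). Residual variance is 1 − r² with one baseline survey and 1 − r²/((1 + r)/2) with the mean of two. At r = .5 these are .750 and .667, ratio .889; at r = .8 they are .360 and .289, ratio .802. Such a participant carries about 80% to 89% of the information of one with both surveys. A withdrawn participant carries none.

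**7. Illustrative bias**, if the Second Survey follows allocation, a fraction f is lost in the pill arm only, and the tendency to be lost correlates ρ = .3 with a poorer baseline-adjusted endpoint (all assumed). Bias = ρ√(1 − r²)·φ(z)/(1 − f), where z is the 1 − f normal quantile. For f = .10, φ(z)/(1 − f) = .1755/.90 = .195, giving .3 × .866 × .195 = .051 SD at r = .5 and .3 × .714 × .195 = .042 SD at r = .7. For f = .20 the factor is .2800/.80 = .350, giving .091 and .075 SD. The direction favours the intervention.

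**The case against.** The strongest reply is that the two sections govern different steps, section 15 continuation and section 9Bii the analysis set, so they can be applied in turn. This does not remove the conflict. Applying section 15 first creates the gaps that trigger section 9Bii, and section 15 rests on a claim about usability that section 9Bii does not share.

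A second reply has more force. No section lists the scales in each survey. The First might hold screening, demographic or physical-health items, and the Second some or all primary-outcome scales. Section 15's reason would then be partly right, because no observed baseline would exist without the Second Survey. This stands. A reader might infer that every such participant is scorable from the First Survey and that the stated reason is simply wrong; the documents do not establish that.

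Third, the bias argument needs the Second Survey to follow allocation. Section 9Bii's Time 2 is a follow-up occasion, but nothing equates it with the Second Survey, and section 15 calls that survey a baseline one. This also stands: the bias is conditional, and the figures in step 7 combine one-sided loss with an assumed correlation. Even so they reach at most .091 SD against a planned d of .60.

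Finally, a reader might infer that the planned power of .80 survives only about 5 losses per arm. That holds only for an unadjusted t-test. Under the planned ANCOVA with r = .5, about 16 losses are tolerable. Fifty is also a minimum, with up to 200 per arm if funding comes.

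**Conclusion.** The conflict is real and does not depend on any assumed rate: missing only the Second Survey leads to retention under section 9Bii and exit under section 15, and neither the SAP nor section 16A reconciles them. Followed as written, section 15 stops data collection on willing people whom the plan's own analysis rule would keep.

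The consequence is conditional. It is a post-randomisation exclusion if the Second Survey follows allocation, and a loss of recruits only if it precedes it. How many are affected cannot be computed. The power, information and bias figures show scale under stated assumptions and predict nothing for this trial; in particular, they do not show that the study is underpowered. The point concerns survey follow-up and the analysis set. It does not dispute the five-day rule or the choice of imputation method. It is worth correcting because the remedy is specific and cheap.

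**What to change.** - In Protocol section 15, state that no randomised participant is withdrawn for a missed survey. They are sent all remaining surveys and analysed in the assigned group.
- Apply any requirement to complete baseline surveys only before allocation. State where each survey falls relative to allocation, which outcome scales it contains, and which analysis time point it supplies.
- In the SAP, define the baseline covariate as the mean of the available baseline surveys where the First Survey contains that outcome scale. Otherwise handle the missing baseline with the planned missing-data method.
- Make sections 9Bii and 15 state one rule, and repeat it in the SAP.

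This needs a few sentences and no new visits, measures or staff. The downside is that a few participants will have a less precise or imputed baseline. The change concerns survey collection and analysis only.

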### 16. Monitoring Plan to Assess Data to Ensure Safety of Subjects.

16A. Is there a monitoring plan to periodically assess the data to ensure the safety of subjects or to ensure negative outcomes do not occur?  No  Yes

Explain your answer. If you answered Yes, describe the monitoring plan.

Yes. [name] will oversee the collect and storage of data and supervise authorize personnel. Data will be reviewed on a weekly basis until data collection is completed. The following conditions will necessitate termination from the study: 1) participant indicates that they are experiencing a significant amount of stress and wishes to pursue a different treatment and 2) participants no longer wish to participate for any reason.

*CLICK IRB: Upload any data safety monitoring plans to the Supporting Documents SmartForm pages.*

16B. If there is a data safety monitoring committee or board, describe the composition and frequency of meetings.  Not Applicable

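### Read literally, Section 16A ends the surveys as well as the pills for a stressed participant who wants other treatment; a small rewording would let willing participants keep answering.

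*Protocol*

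**What the plan says.** Protocol Section 16A answers the safety-monitoring question with a mandatory rule: "The following conditions will necessitate termination from the study". Two conditions follow. The first is that the "participant indicates that they are experiencing a significant amount of stress and wishes to pursue a different treatment". The second is that "participants no longer wish to participate for any reason". The rule refers to the study, not to the pills.

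Other places that bear on it:

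- Section 12D (consent): "Participants will be told that they can withdraw from the study at anytime".
- Section 15 asks about "any anticipated circumstances where the researcher will withdraw subjects from the study regardless of the subject's wishes". The answer names only missed surveys. The First, Second and Fourth are essential, and "They really can only miss the Third Survey".
- Section 9Bii (missing data): "When possible, we plan to use multiple imputation methods to account for missing data", but also "If a participant is missing data from 2 or more time points for our primary outcome, they will be removed for analyses". People who drop out may be asked why and are offered resources; further surveys are not mentioned.
- The SAP fills in missing data by maximum likelihood before the primary ANCOVA. It does not name the variables used and does not repeat the removal rule.
- Section 4B names distress from answering the questionnaires as a risk. Section 4C lets participants skip questions or withdraw, and gives them support resources.

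**The concern.** Stopping a treatment and stopping measurement are different events, and 16A does not separate them. The second condition already releases anyone who wants to go. Taken at its word, the first therefore reaches one further group: people who want other help but are still willing to answer. For them the Fourth-survey endpoint would go unobserved although it could have been collected.

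The reason for the loss is tied to what the trial measures. The SAP's primary outcomes are COVID stress, perceived stress, anxiety and depression. Entry requires a COVID Stress Scale score of at least 35 (Section 11A), and controls receive no treatment, so a participant asking for other help is foreseeable. If such exits fall unevenly between the arms, the observed means no longer compare the groups as randomised. Losing stressed controls would shrink the difference, and losing stressed placebo participants would enlarge it.

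**Working it through.** **What the text does to such a person.** If the exit comes after the Second survey, the Third and Fourth are both missing. If those are Time 2 and Time 3 (a mapping the protocol does not spell out), the 9Bii rule removes the person. If the Third was completed, the Fourth is imputed. Under the SAP either person might be filled in by maximum likelihood. No readable section of either document provides for surveys after a 16A exit.

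**The plan's own figure.** Section 9Bii gives d = .60, power .80, alpha .05 and 50 per arm. A two-sided two-sample t-test needs 45 per arm (44.6 rounded up), and 50 per arm gives power 84.4%. So 50 exceeds what the stated inputs need.

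**Size of the shift (illustration).** From the documents: n = 50 per arm, d = .60. Assumed, because the documents give no values: k people lost from one arm; each z = 1 to 2 SD above that arm's endpoint mean; baseline–endpoint correlation r = .5 to .7.

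- Without baseline adjustment, the shift in the arm mean is kz/(50 − k). k = 1: 1/49 = 0.020 to 2/49 = 0.041 SD. k = 3: 3/47 = 0.064 to 6/47 = 0.128 SD.
- With baseline adjustment: someone z above the endpoint mean is expected to be rz above the baseline mean, so baseline predicts r²z and (1 − r²)z remains. The shift is k(1 − r²)z/(50 − k).
  - k = 0: none.
  - k = 1: 0.51 × 1/49 = 0.010 to 0.75 × 2/49 = 0.031 SD. The .60 becomes .59 to .57 if the person is a control, or .61 to .63 if from the placebo arm.
  - k = 3, all in one arm: 3 × 0.51/47 = 0.033 to 3 × 1.5/47 = 0.096 SD. The .60 becomes .57 to .50, or .63 to .70.
  - Two in one arm and one in the other, with e = (1 − r²)z: 2e/48 − e/49 = 0.011 (e = 0.51) to 0.032 (e = 1.5) SD.
  - Equal numbers with equal z in both arms: zero.
- At the ceiling of 200 per arm, k = 3: 3 × 0.51/197 = 0.008 to 3 × 1.5/197 = 0.023 SD.

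**Power.** 84.4% at 50 v 50, 84.0% at 50 v 49, 83.2% at 50 v 47.

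**Does the fill-in repair it?** That depends on its inputs. If missing endpoints are predicted from arm and baseline alone, the filled values lie on the fitted ANCOVA surface and add no residual, so the group coefficient is the same as after removal. Simulation agreed: the largest difference was 1e-14 over 4,000 data sets. If the model also uses a completed Third survey, r² is replaced by a larger squared multiple correlation and less bias remains. The documents do not say which applies.

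**Cost of keeping these people.** If other treatment gives a 0.5 SD benefit (assumed), each retained participant moves an arm mean by 0.5/50 = 0.010 SD. That is about the low end of the shift from losing one person.

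**The case against.** The strongest reply is that the first condition describes voluntary exit. It depends on the participant's own wish, and Section 15, where forced withdrawal belongs, lists only missed surveys. On that view nobody willing to answer would be turned away. This reading is plausible and cannot be excluded, but 16A does not state it, and listing unwillingness as a second condition points the other way. The consent form and any data safety monitoring plan are separate uploads, were not available, and may settle the matter.

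A second reply is that the clause protects people. Section 4B names the questionnaires themselves as a source of distress, and release from them has value. This stands. A reader might infer that the condition adds nothing except lost surveys; that goes too far.

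A third reply is that materiality is not shown. This also stands. The drop from .60 to .50 needs three losses in one arm and none in the other, each 2 SD above the mean, at the lower correlation. Nothing in the documents supports that count. Follow-up lasts only 17 to 20 days, and people reporting severe mental illness are excluded.

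Two further inferences are tempting and unsupported. One is that the clause biases the trial in a known direction, for or against placebo: the documents say nothing about which arm would lose people. The other is that the planned missing-data methods recover nothing: that holds only for a fill-in from arm and baseline alone, which the SAP does not specify.

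**Conclusion.** The point holds as a minor, cheap improvement. Read literally, the first condition ends surveys for people who want other treatment but would still answer, and no readable text restores their follow-up. The loss is related to the outcome, and imputation may recover it only partly. Its size and direction cannot be judged from the documents, and it may affect nobody. The illustrative shifts of 0.010 to 0.031 SD for one loss and 0.033 to 0.096 SD for three in one arm rest entirely on the assumed k, z and r; the power effect is negligible. The documents do not support calling this a serious threat to the primary comparison. Nor does the point cover the other routes to a missing endpoint, such as withdrawal under the second condition or five days without response.

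**What to change.** Replace the first condition in 16A with wording to this effect: a participant in either arm who reports significant stress and wishes other treatment may stop the placebo pills, if assigned; receives the resources in 4C; has any other treatment and its start date recorded; and is invited, without pressure and free to skip questions or withdraw, to complete the remaining surveys, above all the Fourth. Leave the second condition unchanged. In the SAP, analyse these participants as randomised, report their number by arm, and state which variables the fill-in uses.

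The cost is an IRB wording amendment, one survey item on other treatment, and a consent line if the form does not already cover this. There are two downsides:

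- **Dilution.** The estimate will include some people who took other treatment, about 0.01 SD in an arm mean per person under the assumption above. If they are mostly controls, this too shrinks the difference, hence the report by arm.
- **Burden.** A distressed person is asked further questions. The skip and withdrawal options in 4C limit this but do not remove it.

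The SAP is written in the past tense. If data collection has ended, what remains useful is to report exits under the first condition by arm, with the last survey each person completed.
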